7.4. Study Procedure

Patients will be enrolled in the study for up to fifteen (15) weeks, including twelve (12) weeks for active monitoring. The study timeline for all procedures is defined in the Section 17 table. All patients enrolled in the study, following the collection of a verbal informed consent, will have a medical history recorded by phone. Upon confirmation of basic eligibility, patients will be sent a telemonitoring system consisting of the GoSpiro®, a pulse oximeter and a GoHome tablet. A member of the Clinic research staff will schedule a (virtual (phone or video) appointment with the patient for when the system has arrived. They will train each patient on how to use the devices and will instruct the patient how and when to record measurements. Pulse oximetry (SpO2 and HR), as well as slow and forced spirometry with the GoSpiro will be collected during this training call. These instructions will also be provided on patient information material (See Appendices A and B). Patients should exhibit proficiency with the devices and demonstrate understanding of the measurement schedule prior to ending the call.

The study nurse will contact the patient the following day by phone to confirm that the patient is able to set up the GoHome and use the devices for measurements. In the event the participant is not able to provide and transmit satisfactory data collection after one week (due to technical or training reasons) they will be removed from study and replaced with another participant toward the total recruitment goal. The study nurse will call the patient every four (4) weeks to collect information on any changes to inhaled medication, steroids or antibiotics and assist the patient with any operational questions. Between phone calls, Clinic research staff or device manufacturer's support personnel will be available to assist the patient should questions or technical issues arise. The study nurse will conduct a final phone visit to collect close out data prior to the participant returning the devices (see Section 17).

Physiologic data from the patients will be transmitted automatically following each measurement and will be available on the CarePortal within a few minutes of its collection. Physiologic data (spirometry and oxygen saturation) will be collected every day. Medication reminders, COPD Action Plan communications, etc. will be sent every day if scheduled. In addition to monitoring parameters, health

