teaching tips as part of the COPD Action Plan will also be incorporated into the GoHome software to educate and motivate patients regarding self-care. A Quality of Life questionnaire (COPD Assessment Test) will also be collected every 4 weeks from the patients through the GoHome tablet.

At the end of study (after completion of final phone visit), the patients will return the equipment to UNC via a pre-paid FedEx air bill that has been included with the original shipment. A member of the Clinic research study team will have a final call with the patient to check on the patient's respiratory status and have them complete a usability questionnaire by phone.

8. Quality Control Measures

Quality control of the lung function measurements will include automatic ATS/ERS intra-measurement grading of the forced flow-volume loops and slow spirometry to ensure interpretable and actionable home spirometry.⁵ MTI will assist with determining the number of missed spirometry sessions with seven times per week testing, and determining any technical issues in transmission of data from the spirometer to the MTI CarePortal.

The GoSpiro home spirometer meets the 2019 ATS/ERS criteria for accuracy and reproducibility.⁵ Baseline pulmonary function will be defined as the mean FEV1 over the first two weeks of the study (six measurements). If older data is available for the patient, that data may be included in establishing historic values for analysis. Variability of pulmonary function for alerts to Clinic staff will include a decrease by one personalized z-score using pulmonary function measurements for an individual patient and calculated over the length of the study as well as using historic data if available.

Alerts from acute declines in pulmonary function will be defined as any decrement in either FEV1, FVC or IC >10%. Oxygen saturation readings below 88% will trigger an alert. For patients being managed with DPI delivered inhaled drugs, monitoring of peak inspiratory flow for detection of inadequate flows to aerosolize and deliver the powder, will also generate alerts. The MTI CarePortal will provide daily reports to the Clinic research staff of patient trending towards alert levels, as well as patients with low adherence to medications or measurements.

9. Assessments

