The secondary endpoints will be reported as proportion with 95% confidence interval of participants with score of 4 or higher on individual survey domains of patient satisfaction summary score; Descriptive analysis of patient satisfaction summary scores will include mean (SD), median (IQR), range of scores.

For the COPD exacerbation analyses, the proportion of patients with COPD exacerbations and the rate of exacerbations occurring during follow-up will be reported along with 95% CI. A patient will be considered censored for exacerbations at the time of the last documented visit, the end of the study, or death (whichever occurs earlier), if they did not experience an exacerbation before.

Exploratory Endpoints Definitions

The study contains exploratory endpoints to examine individual components of the monitoring functions and their impact. These include:

- Rate of self-reported COPD exacerbations stratified by FEV1 and defined as the 30-day COPD exacerbation rate, defined as the mean number of self-reported COPD exacerbations

requiring treatment with antibiotics or steroids per 30 days of follow-up (averaged using 3 months of follow-up data), stratified by FEV1 (separately <50% predicted and >=50% predicted).

- Home spirometry measurement collection adherence defined as the percentage of participants achieving >50% completion of spirometry measurements over three months.
- Home pulse oximetry measurement collection adherence defined as the percentage of participants achieving >50% completion of pulse oximetry over three months.
- Home questionnaire collection adherence defined as the percentage of participants achieving >50% completion of home questionnaires over three months.
- Quality of home forced spirometry measures defined as the percentage of forced home spirometry measurements that meet ATS quality standards
- Change from baseline on COPD Assessment Test (CAT) Total Score defined as the CAT scores measured at baseline, week 4, week 8 and week 12 and the median (SD) change in CAT score from baseline will be calculated at each time point.
- Inspiratory Capacity variability defined as the coefficient of variation will be calculated by dividing standard deviation of Inspiratory Capacity values by the mean of the inspiratory capacity values. Inspiratory capacity measured via slow vital capacity maneuver will be performed at home five days per week during duration of study.

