- Inspiratory Capacity before, during and after COPD exacerbations defined as the overall median Inspiratory Capacity reported at three time intervals: the week before COPD exacerbation, the week of COPD exacerbation, and the week after COPD exacerbation.
- Number of clinical interventions defined as the total number of clinical interventions per participant over study duration. Clinical interventions will be categorized into one of three types (phone contact, clinic visit, referral to Emergency Department).
- Type of clinical interventions defined as the percentage of type of clinical intervention across all study participants. Clinical interventions will be categorized into one of three types (phone contact, clinic visit, referral to Emergency Department).
- Suboptimal peak inspiratory flow measurements defined as the percentage of peak inspiratory flow measurements <3.27 liter/sec obtained on forced spirometry maneuvers.
- Maintenance inhaler adherence defined as the adherence will be defined by average number of days per week (range 0-7) participant reports maintenance inhaler use.
- Change from baseline in maintenance inhaler adherence defined as the change from baseline to 3 months in maintenance inhaler adherence. Adherence will be defined by number of days per week (range 0-7) participant reports maintenance inhaler use.
- Change from baseline in rescue inhaler use defined as the change from baseline to 3 months in rescue inhaler use. Rescue inhaler use will be categorized at baseline and 3 month visit as not at all, once a week or less, 2-3 times per week, 1-2 times per day, 3 or more times per day.

Analysis of Exploratory Endpoints

The exploratory endpoints will be analyzed as described below. The hypothesis testing of these additional secondary efficacy endpoints is considered exploratory. All tests with p value < 0.05 will be interpreted nominally as statistically significant.

- For stratified COPD exacerbation analyses, the proportion of patients with COPD exacerbations and the rate of exacerbations occurring during follow-up will be reported along with 95% CI stratified by FEV1 severity (<50% predicted: >=50% predicted).
- Individual home assessment component adherence will be reported as proportions with 95% confidence intervals
- Quality of home forced spirometry measures will be reported as proportions with 95% confidence intervals

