- Descriptive analysis of change from baseline to weeks 4, 8 and 12 on CAT Total score including mean (SD), median (IQR), range
- Descriptive analysis of Inspiratory Capacity measurements, including mean (SD), median (IQR), range, coefficient of variation
- The overall median of Inspiratory Capacity in the week before, of, and after each exacerbation will be calculated and compared using Kruskall-Wallis testing.
- The total number and distribution of type of intervention (phone contact, clinic visit, referral to Emergency Department) will be summarized in tabular format
- The proportion of suboptimal peak inspiratory flow measurements (defined as <3.27L/sec) will be reported with 95% CI. Additional exploratory analyses include distribution of peak inspiratory flow measurements along with proportions of alternative thresholds.
- Descriptive analysis of overall maintenance inhaler adherence including mean (SD), median (IQR), range, proportion and 95% CI of participants with >50% adherence
- Descriptive analysis of change from baseline to week 12 on number of days per week of maintenance inhaler adherence including mean (SD), median (IQR), range
- Tabular summary of overall rescue inhaler use (categorized into not at all, once a week or less, 2-3 times per week, 1-2 times per day, 3 or more times per day)
- Comparative analysis (chi square) of distribution of categorical responses to rescue inhaler use comparing baseline to 12 week visit
- Tabular summary of number and type of SAE

14. Safety Monitoring

As this study is deemed low risk, using technology frequently prescribed for use by COPD patients at home, oversight for this feasibility study will be conducted by the PI ([name]). The PI will monitor data to ensure the safety of participants. Only treatment-related serious adverse events (SAEs) will be reported to the IRB using the Adverse Event Template Form, per institutional and national guidelines within one business day of notification of the event. Hospitalization for COPD exacerbation will be considered an SAE. SAEs will be tracked for 30 days following termination of the study.

15. Administrative Requirements

15.1. *Ethical Considerations*

The study will be conducted in accordance with the ethical principles founded in the Declaration of Helsinki, and according to local applicable laws and regulations. The institutional

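### Exacerbations near the start or end of monitoring can lack home Inspiratory Capacity in one of the three comparison weeks, and the planned comparison of overall medians ignores the pairing within events.

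*Combined protocol and SAP*

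**What the plan says.** Section 13 (exploratory endpoint definitions) asks for this summary: "overall median Inspiratory Capacity reported at three time intervals: the week before COPD exacerbation, the week of COPD exacerbation, and the week after COPD exacerbation". The matching analysis line reads: "The overall median of Inspiratory Capacity in the week before, of, and after each exacerbation will be calculated and compared using Kruskall-Wallis testing". The same part of Section 13 adds: "All tests with p value < 0.05 will be interpreted nominally as statistically significant".

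The readings come from home slow spirometry: "Inspiratory capacity measured via slow vital capacity maneuver will be performed at home five days per week during duration of study". Section 7.4 limits the monitored period: "Patients will be enrolled in the study for up to fifteen (15) weeks, including twelve (12) weeks for active monitoring". The slow-spirometry row in Section 17 is marked for weeks 1 to 12, with nothing at screening or in week 13. The first slow test is at the week-1 training call: "Pulse oximetry (SpO2 and HR), as well as slow and forced spirometry with the GoSpiro will be collected during this training call".

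An exacerbation is a self-reported event treated with antibiotics or steroids (Section 13). The plan gives no rule for dating its onset. It does not say whether a week is a study week or seven days counted from onset. It sets no minimum number of readings, does not say what to do when an interval is empty, and does not require the three medians to use the same events.

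**The concern.** The endpoint needs readings in three consecutive weeks around each event, but the schedule guarantees them only for events away from the edges of the 12 weeks. If one event is absent from one interval, that interval's overall median rests on a different set of patients. Patients are likely to differ far more in their usual Inspiratory Capacity than one patient varies from week to week. With few events, a gap between two of the medians may therefore reflect who contributed and not any change around the exacerbation.

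Kruskal-Wallis adds to the problem. It treats the three weeks as three independent groups, although they are repeated measurements on the same events. The spread between patients then counts as noise in the comparison.

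Section 5.2 and the synopsis list the relation between change in slow spirometry and exacerbation as an endpoint, and Section 13 says the results will inform the power of later studies. At stake is whether this exploratory contrast can be interpreted and carried forward.

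**Working it through.** The plan states no event count, power or effect size for this endpoint, so there is no figure of its own to reproduce.

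**Inputs from the documents.** 12 patients (Section 6); 12 weeks = 84 days of monitoring (Section 7.4); slow spirometry on Sunday, Monday, Wednesday, Friday and Saturday (Sections 9.2.3 and 17).

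**Assumptions, not in the documents.** Onset uniform over the 84 days; 1 to 3 exacerbations per patient-year; mean Inspiratory Capacity 2.0 L; between-patient SD 0.5 L (range 0.3 to 0.7); day-to-day SD 0.15 L; each event from a different patient.

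**1. Study weeks.** An event in week 1 has no scheduled week before. An event in week 12 has no scheduled week after. Weeks 2 to 11 are complete. Share incomplete: 2/12 = 16.7%.

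**2. Rolling 7-day windows.** Three full windows need onset on days 8 to 71, which is 64/84 = 76.2% of days. Counting scheduled tests and averaging over the seven possible starting weekdays, 23.1% of onset days leave some interval with fewer than five tests, and 10.2% leave one with none. Nearly all the empty ones come from the last week. In the first week the window before onset is mostly short, not empty.

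**3. Chance that it happens.** Exposure is 12 × 84/365.25 = 2.76 patient-years, so m = 2.76, 5.52 or 8.28 expected events at 1, 2 or 3 per year. With f the incomplete share, P(at least one) = 1 − exp(−m·f).
- Study weeks, f = 1/6: m·f = 0.46, 0.92, 1.38, so P = 37%, 60%, 75%.
- Rolling, empty interval, f = 0.102: P = 25%, 43%, 57%.
- Rolling, short interval, f = 0.231: P = 47%, 72%, 85%.

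**4. Effect on the medians.** Simulation with no true change, 6 events, five readings a week, study-week reading. Each interval's overall median is taken over the event-week medians available.

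| After minus before | SD, overall medians | SD, within event |
|---|---|---|
| Edge weeks missing | about 0.15 L | about 0.06 L |
| No week missing | about 0.07 L | about 0.05 L |

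For between-patient SDs of 0.3 to 0.7 L, the SD as written is 0.11 to 0.20 L, and the within-event SD stays near 0.06 L. The distribution has heavy tails: the typical (median) absolute shift with edge losses is 0.07 to 0.08 L, against 0.05 L with complete data.

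**5. When one event does lose its week after.** With 3 to 6 events, between-patient SD 0.4 to 0.8 L and a week-to-week SD of 0.1 L, the chance that the after and during medians differ by more than 0.2 L with no true change rises from 2%–14% to 15%–62%.

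**6. The test.** With 6 complete events and an assumed 0.2 L fall in the week of the event (SDs as in step 4), Kruskal-Wallis on the event-week medians gives p < 0.05 in under 1% of runs; Friedman does so in about 90%. With no fall, Friedman rejects in about 5% and Kruskal-Wallis in essentially none.

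**7. Hospital stays.** Under rolling windows, a stay of 2 to 5 days from onset leaves 1 to 4 scheduled slow tests in the onset week. Only a stay covering the whole week leaves none.

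**The case against.** A reader might infer that exacerbations treated in hospital always lose the week of the event, so that the result covers mainly mild events. The documents do not support that. Section 14 says only "Hospitalization for COPD exacerbation will be considered an SAE". Nothing says that spirometry stops in hospital or gives a length of stay, and step 7 shows that a short stay need not empty the week. Hospital loss is possible, not established.

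A reader might also infer that the three medians will come from different events. They will only if an incomplete event occurs, and step 3 makes that likely but not certain. Under rolling windows most first-week onsets still have some earlier readings. Week-13 readings are unscheduled but not impossible, because patients keep the device until the final call: "At the end of study (after completion of final phone visit), the patients will return the equipment to UNC".

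The analysis line refers to each exacerbation, which could be read as scoring per event. Section 13 also plans paired t-tests for important continuous variables at two times and names changes in Inspiratory Capacity among the items to be reported. Neither settles the matter. The definition still calls for one overall median per interval, the named test still assumes independent groups, and the general provisions are not tied to exacerbations.

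The sizes rest on assumed event rates and SDs, and the SD in step 4 is larger than the typical shift suggests. That stands. So does the point that no primary result or participant safety depends on this endpoint, and that a handful of events could be listed one by one.

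**Conclusion.** The concern holds as a minor point. By study week, 16.7% of uniformly timed events have no scheduled readings in one of the three intervals. With rolling windows, about 10% have an empty interval and 23% a short one. At an assumed 1 to 3 events per patient-year, the chance of at least one such event is 25% to 85% across these readings. The overall medians may then describe different events and patients, and under the assumptions in step 4 the after-minus-before difference is about two and a half times as variable as the within-event difference (0.15/0.06 = 2.5). This is added noise and not bias: in that simulation neither summary is shifted on average when there is no true change.

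The mismatch between Kruskal-Wallis and paired data does not depend on any week being missing. With complete windows the test would almost never detect the assumed fall, so a non-significant result would say little.

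The event rate, the mean, both SDs and the 0.2 L fall are illustrations. The schedule counts in steps 1 and 2 need only the document inputs and, to be read as shares of events, uniform onset.

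**What to change.** In Section 13, amend the exploratory definition and its analysis line as follows.

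- Define the onset date and the three 7-day windows relative to it, and set a minimum number of readings per window.
- Take each event's median in each window. Report the within-event differences (week of minus before, after minus before) as median and range over the events scorable in both windows.
- Replace Kruskal-Wallis with a paired method, labelled exploratory: for example Friedman on events with all three windows, or a mixed model with patient and event effects. With very few events, rely on the listed differences. The smallest exact Friedman p-value is (1/6)¹ = 0.17 with two complete events and (1/6)² = 0.028 with three.
- Give the number of events and patients in each comparison, and the unscorable events by reason (start of monitoring, end of monitoring, hospital stay, missed sessions).

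The cost is SAP wording and a little programming. No new measurement is needed, but onset dates must be recorded if the case report form does not already capture them. The downside is that some events leave one or both comparisons: about 17% to 23% from timing alone if complete windows are required, plus any lost to hospital stays or missed sessions.

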Differences between important continuous variables at two specific times will be evaluated with the two-sided paired t-test ($P<0.05$). Important categorical events such as changes in FEV1, Inspiratory Capacity, QoL, medication adherence, rehospitalization and incidence of adverse events will be evaluated by constructing 95% confidence limits in their incidence, and also with descriptive statistics. In addition, the results will be used to identify technological deficiencies and provide data to inform the power requirements for future studies.

Primary Endpoint Definitions

The first primary endpoint variable for this study is the change from baseline in Total Score of COPD Assessment Test (CAT). The total CAT score is calculated by summing the scores of all items and ranges from 0 to 40, higher scores indicating severe condition. The change will be calculated as the CAT score at Week 12 minus the CAT score at Enrollment. A negative change in CAT score will indicate an improvement in patient status.

The second primary endpoint variable for this study is adherence to performing scheduled measurements and responding to scheduled questionnaires. For each subject the adherence will be recorded based on the data uploaded to the CarePortal. The adherence percentage will be calculated by the difference in recorded measurements and answered questionnaires versus the scheduled measurements and questionnaires.

Analysis of Primary Endpoints

The primary outcomes will be reported as proportions with 95% confidence intervals, on the FAS.

Secondary Endpoint Definitions

The prespecified secondary endpoints for this study will include:

- Participant satisfaction survey scores at 3 months (Time frame: 3 months) defined as the percentage of participants with score of 4 or higher on individual survey domains. A satisfaction survey (investigator-developed, 15 questions, each question is graded on a scale of 1-5, 1 being not at all and 5 being extremely) will be used to measure home spirometry and table ease and usefulness.
- Rate of self-reported COPD exacerbations (Time frame: 3 months) defined as the 30-day COPD exacerbation rate, defined as the mean number of events/30 days of follow-up (using three months of follow-up data). COPD exacerbation events are defined as self-reported COPD exacerbations requiring treatment with antibiotics or steroids.

Analysis of Secondary Endpoints

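### Minor: two exploratory tests in Section 13 (Kruskal-Wallis for Inspiratory Capacity around exacerbations, chi-square for rescue inhaler use) assume independent groups although both comparisons are within-patient, so their p-values are not calibrated

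*Combined protocol and SAP*

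**What the plan says.** All of this is in Section 13.

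- **Inspiratory Capacity, definition:** "Inspiratory Capacity before, during and after COPD exacerbations defined as the overall median Inspiratory Capacity reported at three time intervals", namely the weeks before, of and after the exacerbation. The item just above it gives the measurement frequency: "Inspiratory capacity measured via slow vital capacity maneuver will be performed at home five days per week during duration of study".
- **Inspiratory Capacity, analysis:** "The overall median of Inspiratory Capacity in the week before, of, and after each exacerbation will be calculated and compared using Kruskall-Wallis testing".
- **Rescue inhaler use, definition:** the endpoint is a change from baseline to 3 months. "Rescue inhaler use will be categorized at baseline and 3 month visit as not at all, once a week or less", with three further categories of rising use, so five ordered categories in all.
- **Rescue inhaler use, analysis:** "Comparative analysis (chi square) of distribution of categorical responses to rescue inhaler use comparing baseline to 12 week visit".
- **Reading of the results:** "All tests with p value < 0.05 will be interpreted nominally as statistically significant".

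Two general sentences earlier in the section might be thought to cover the matching. The first is "Differences between important continuous variables at two specific times will be evaluated with the two-sided paired t-test". The second begins "Important categorical events such as changes in FEV1, Inspiratory Capacity, QoL, medication adherence, rehospitalization" and promises 95% limits on incidence. Neither reaches these comparisons. The first is for continuous variables at two times, while here there are three weeks in one case and ordered categories in the other. The second treats a change in Inspiratory Capacity as a categorical event but gives no cut-off for it.

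**The concern.** The study follows twelve patients and describes no comparison group. The three weeks around an exacerbation belong to one patient, and the two rescue-use responses come from the same person. Kruskal-Wallis and Pearson chi-square treat such values as unrelated. Differences between patients then count as noise in the comparison, and the reference distribution no longer applies.

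The plan also does not say what enters the Kruskal-Wallis test. The definition speaks of an overall median at three intervals, while the analysis line speaks of each exacerbation. Three readings are possible: one number per interval, one median per exacerbation-week, or all daily readings pooled by week.

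Two things are at stake. A real fall in Inspiratory Capacity around exacerbations, or a consistent shift in rescue use, could be reported as no difference. If daily readings are pooled, a chance difference could be labelled nominally significant. The plan also wants its results to inform the power of later studies, and an analysis that ignores the pairing misstates the variability needed for that.

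**Working it through.** The documents give no error rate, power, SD or effect for either test, so there is no figure of the plan's own to reproduce.

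**Inputs from the documents.** 12 patients, 3 months each, slow spirometry five days a week, five rescue-use categories, threshold 0.05.

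**Assumptions.** The entry criteria require one hospitalization or two outpatient exacerbations in the prior 12 months. If those rates continued, the expected number of events is 12 × 1 × 3/12 = 3 to 12 × 2 × 3/12 = 6. I take one event per patient. A daily reading is a patient effect (SD 0.4 or 0.6 L) plus a patient-week effect (weekly SD 0.12, 0.2 or 0.3 L) plus daily noise (SD 0.15 L). This one model is used for everything under steps 2 and 3. It was simulated with 40,000 data sets per setting, using the usual chi-square approximation for Kruskal-Wallis.

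**1. One overall median per interval.** Three distinct values have ranks 1, 2, 3, so H = 12/(3 × 4) × (1 + 4 + 9) − 3 × 4 = 2. On 2 degrees of freedom p = exp(−2/2) = 0.368, whatever the data. The test can never reject.

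**2. One median per exacerbation-week.** Kruskal-Wallis type I error is at most about 0.006 in every setting with 3 to 6 events. A separate simulation with no within-patient correlation gave 0.041 to 0.050 at 4 to 12 events, so the loss comes from the matching that the test ignores. For a 0.3 L fall in the exacerbation week only, power is:

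| Weekly SD | Exact Friedman at 3/4/5/6 events | Kruskal-Wallis |
|---|---|---|
| 0.12 L | about 17/41/63/64% | about 0.4–6% |
| 0.2 L | about 10/23/33/33% | about 0.4–6% |

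Exact Friedman critical values (with size) at 3/4/5/6 events, by enumeration, are 6.0 (0.028), 6.5 (0.042), 6.4 (0.039) and 7.0 (0.029).

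**3. Daily readings pooled by week.** Kruskal-Wallis type I error over 3 to 6 events:

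| Weekly SD | Between-patient SD 0.4 L | Between-patient SD 0.6 L |
|---|---|---|
| 0.12 L | 3–7% | 1–4% |
| 0.2 L | 12–18% | 5–11% |
| 0.3 L | 25–31% | 14–22% |

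The error runs from conservative to clearly inflated. It is inflated when week-to-week variation is large relative to the daily and between-patient variation.

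**4. Rescue use.** There are at most 24 responses in a 2 × 5 table, so the mean expected count is at most 24/10 = 2.4. With no true change and 12 patients, simulated chi-square type I error is about 0.04 at a within-patient correlation of 0, 0.020 at 0.5, 0.014 at 0.7 and 0.005 at 0.9.

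As an illustration, let the baseline counts be 0, 2, 3, 4, 3 from least to most use, and let all 12 patients improve by one category, giving 2, 3, 4, 3, 0. The expected counts per row are 1, 2.5, 3.5, 3.5, 1.5. Then χ² = 2 × (1²/1 + 0.5²/2.5 + 0.5²/3.5 + 0.5²/3.5 + 1.5²/1.5) = 5.49 on 4 degrees of freedom, p = 0.24. The two-sided sign test gives 2 × 0.5¹² = 0.0005.

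With 9 improving and 1 worsening, chi-square gives 0.09 to 0.65 over all allocations, against a sign-test p of 0.021. With 7 improving and 2 worsening, the median chi-square p is 0.64 and the sign test gives 0.18, so the matched test is not decisive there either.

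If chi-square were run on the 5 × 5 baseline-by-week-12 table instead, it would test association and not change. With no shift at all it rejected in 7% to 46% of simulations at correlations of 0.5 to 0.9.

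**The case against.** **Both tests are exploratory in a 12-patient study that declares itself unpowered.** This stands, and it sets the severity. Descriptive summaries of both variables are planned, and no primary endpoint or safety rule depends on either p-value. Section 5.2 does list the slow-spirometry and exacerbation item as secondary, and a reader might infer that a secondary result is affected. The synopsis and Section 13 place it among the exploratory endpoints, and Section 13's own list of secondary endpoints omits it.

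**The plan says only chi-square, and paired tests such as Stuart-Maxwell or Bowker also carry that name.** This stands in part. Pearson is the natural reading of a comparison of two distributions, but that is an inference. If a paired variant was meant, the text needs to say so.

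**The matched test may be inconclusive too.** This stands. At 3 or 4 events exact Friedman power is 10% to 41% in the settings above, so changing the test would often leave the conclusion unchanged.

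**The inflation depends on chosen SDs.** This stands. With daily SD 0.30 L, weekly SD 0.2 L and between-patient SD 0.6 L, the pooled type I error is 4–7%, against 5–11% at daily SD 0.15 L. A reader might infer that the plan will produce false positives, or that the unit alone fixes the direction of the error. The documents support neither. Only pooling can inflate the error, and then only under some variance splits.

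**Conclusion.** The mismatch between test and design holds and depends on no assumed SD. Two within-patient comparisons are assigned tests for independent groups (for chi-square, on its natural Pearson reading), and nothing else in Section 13 supplies a matched analysis. Because the plan reads p below 0.05 as nominally significant, the missing calibration affects what may be reported.

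The size for Kruskal-Wallis depends on the reading: no possible rejection, a type I error of at most about 0.6%, or about 1% to 31%. The last two ranges rest on the assumed SDs, 3 to 6 events and one event per patient. Chi-square on the 2 × 5 table errs on the conservative side, ignores the order of the categories and has sparse cells. It can miss a consistent shift but does not manufacture one.

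The severity is minor. Confidence is high in the qualitative point and limited for the individual percentages.

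**What to change.** **Inspiratory Capacity.** Define one value per exacerbation-window: the patient's median for that week. Make the within-patient change with its 95% CI the main result. If a test is kept, use an exact Friedman test blocked on the exacerbation. Use a mixed model with a patient random intercept if a patient has repeat exacerbations or missing weeks. State that with about 3 to 6 events the result may be inconclusive. The half-width of the interval for a change between two windows is t(n−1) × √2 × s/√n, where s is the total within-patient SD of a weekly median. At s = 0.12 L that is 4.303 × 1.414 × 0.12/√3 = 0.42 L with 3 events and 2.571 × 1.414 × 0.12/√6 = 0.18 L with 6.

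**Rescue use.** Replace chi-square with an exact Wilcoxon signed-rank or sign test on the ordered categories, and show a baseline-by-week-12 shift table.

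**Cost.** Two lines of analysis text and one definition. The data are the same and the procedures are standard.
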